### Exclusion criteria

- PCP does not agree to participate.
- Not seeing a general primary care population with at least 20% of Veterans eligible for the study (e.g., will exclude Geriatrics, MH, ID, and HBPC)
- PCPs with less than 250 patients

Identifying and Recruiting Veterans – Using the Veterans Health Information Systems and Technology Architecture (VISTA), the VA's Health Information Technology system, we will continuously identify Veterans who meet the eligibility criteria below. Research staff will review charts to confirm eligibility and send lists to their PCPs who will identify other contraindications to participating. One to two weeks before their potential baseline visit, potential participants will be sent a letter signed by the Principal Investigator (PI) describing the study and giving them the opportunity to opt out (i.e. request not to be contacted). We will then call Veterans to recruit, screen for eligibility, and schedule the baseline visit which allows enough time for all intervention components to be completed. A similar recruitment strategy was used in the VA PROVE study, as well as in our focus group recruitment. We have IRB approval to use this strategy, and successfully recruited Veterans using this protocol in our pilot studies. We will aim for 20% of our sample to be comprised of women so that we can explore whether the intervention needs to be tailored differently for women. To oversample women, we will contact a random sample of eligible male Veterans and all eligible female Veterans consecutively (in a 5:1 ratio). With consultation from local and national leaders in women's health research, we will provide tailored recruitment materials, monitor recruitment targets, and make iterative changes to our recruitment strategy if these targets are not met.

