### Exclusion Criteria (note that we are no longer excluding Veterans with specific health issues)

- Non-Veterans
- A documented current history of active psychosis or other cognitive issues via ICD-10 codes
- Has participated in  $\geq 4$  MOVE! sessions in the past year
- Pregnancy

- PCP stating that Veteran should not participate
- Self-reported inability to read at a 5th grade level due to literacy level or vision problems

With an expected 20% participation rate (based on pilot data) and a 75% retention rate (based on rates from another VA study and other technology-based interventions), we will need to screen 2,615 Veterans with overweight/obesity to enroll a baseline sample of up to 520 Veterans and end with 392 Veterans completing the study. With a screening rate of approximately 30-35 Veterans per week (6 women, 24 men), we will be able to recruit our target population by the middle of Year 3 (recruitment will start the first quarter of Year 2).

Study Arms/Randomization – Under the direction of the study statistician, the PACT teams will be randomized at the provider level using a random number generator to either the PAL Intervention or Enhanced Usual Care intervention arms.

- *PAL Intervention group:* Participants will arrive and complete consenting materials, a Baseline Survey, and the GEM tool. They will then have a brief break if needed. After the break, they will work collaboratively with the Health Coach using tool-generated materials to modify their goals into SMART goals (specific, measurable, attainable relevant, and timely). The patient will then receive materials containing an individualized report with a summary of their personalized advice, initial goals, and barriers and facilitators to weight loss. They will also receive a packet of MOVE! handouts tailored to their questionnaire responses and schedule 10-12 follow-up health coaching phone calls during the next 12 months of intervention. The Health Coach will also inform the patient of the resources available to them at the VA (e.g. MOVE, TeleMOVE!) that can assist them in achieving their goals.

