During the baseline visit we will encourage patients to sign-up for MyHealtheVet, if they have not already done so. If patients are signed-up for MyHealtheVet, they can choose to receive reminders for their upcoming study visits or health coach phone calls electronically via myHealtheVet. Alternatively, patients can choose to receive reminder phone calls from secure VA phones lines. Before upcoming phone coaching calls and study visits, we will send reminders via the secure messaging system MyHealtheVet or make phone calls via secure VA phone lines.

At the end of the visit, the Health Coach will enter a research note into the CPRS system detailing the patient's goals and other important information in the form of a provider report for the provider to review (generated by the tool). At a later date, the patient will meet with a PACT member (either the PCP or another participating PACT member) during their regularly scheduled PC visit who will review the goals and agree on them and/or modify their goals based on a collaborative discussion and conduct brief motivational interviewing to address potential barriers (3-5 minutes). The PACT member will summarize this interaction in a specific CPRS note. Also, over the next 12 months of the intervention, the PACT teamlet will receive CPRS reminders to discuss the goals with the patients when they return for their regularly scheduled PC visits. Patients will follow up with VA resources if indicated/desired. PAL intervention participants will return for separate 6 and 12 month follow-up study visits to measure intermediate behavior change and weight outcomes.

If circumstances restrict the availability of in-person visits (e.g. COVID-19) or based on Veteran's preference, this study will provide a remote/tele-visit option for the baseline, 6 and 12 month follow up visits. For the remote baseline visit, a scale, a tape measure for the waist circumference, informed consent form documents, and the study resource materials will be mailed to the participant. Participants who enroll via a remote visit will have IRB approval for written consent documentation to be waived and a verbal assent will be obtained through telephone/video confirmation by reading the informed consent form to the participant. Through the verbal assent process, the study will document in the patient's medical records on the willingness to be contacted for future research about similar weight loss management research.

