- *Enhanced Usual Care:* Participants will complete the same consenting materials and Baseline Survey as the intervention group. Instead of the completing the PAL tool and receiving health coaching, they will receive

weight management handouts (Healthy Living Messages handouts and MOVE! handouts) as well as information about intensive weight management programs at the VA including MOVE! Participants will follow-up with their PACT teamlets as needed when they return for their regularly scheduled PC visits. Patients will follow up with VA resources if indicated/desired. Enhanced Usual Care participants will return for separate 6 and 12 month follow-up study visits to measure intermediate behavior change, and weight outcomes.

If circumstances restrict the availability of in-person visits (e.g. COVID-19) or based on Veteran's preference, this study will provide a remote/tele-visit option for the baseline, 6 and 12 month follow up visits. For the remote baseline visit, a scale, a tape measure for the waist circumference, the informed consent forms, and the resource materials will be mailed to the participant. Participants who enroll via a remote visit will have IRB approval for consent documentation to be waived and verbal assent will be obtained through telephone/video confirmation by reading the informed consent form to the participant. Through the verbal assent process, the study will document in the patient's medical records on the willingness to be contacted for future research about similar weight loss management research.

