Tailoring the PAL Intervention for Participants with Diabetes– We will use data from Veterans with diabetes from prior pilot studies (unpublished data) and input from our Executive Committee to develop additional diabetes-related content. We will also revise the health coach curriculum to include common counseling needs and concerns for patients with diabetes and linkages to diabetes resources at the VA. [name], RD, the MOVE! coordinator, and [name], a behavioral psychologist and Health Behavior Coordinator (HBC) at the VA NYHHS, both Co-Is, will help create the content and curriculum.

PACT Team Training – PACT team staff will receive training sessions during Year 1 of the study with follow up training by Drs. [name] (PI) and [name] (Co-I). As part of her role as HBC, [name] has provided the majority of RN care managers and PCPs 2-4 hours of MI training, as well as 6 hours of TEACH for Success Health Coaching Course during the past 4 years. We will build upon this VA training to include 5As-based obesity counseling and additional MI skills practice based on a 5As training intervention conducted by [name] and other adapted MI materials through CCMI. We will invite PACT staff to observe MOVE! sessions since we and others have found that clinicians often lack knowledge about program specifics which negatively impacts referrals. Training will also include indications and processes for referring to bariatric surgery. The first training will be approximately one hour with 2-3 subsequent trainings for 15-30 minutes. We will provide an overview of the 5As and the intervention components and practice brief MI (using role playing) to support Veterans' weight management goals and address barriers to change. Finally, we will assist in incorporating the health coach into each PACT team (e.g., include health coach at monthly PACT team meetings). We will use an academic detailing approach scheduled either one-on-one or in small groups so as not to interfere with VA clinical or administrative duties. This delivery approach is well accepted and similar to that used in the PROVE study.

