## Data Collection

Veterans: Assessment will occur at the following time points:

- In person study visits at Baseline, 6, and 12 months: Veterans will meet with research staff to complete surveys (described below), weight, height (Baseline only), blood pressure and waist circumference measurement, and blood tests (Baseline, 6, and 12 months only). If circumstances restrict in-person visits (e.g. COVID or if Veteran opts for a remote visit, the weight and waist circumference will be obtained via telephone/video. Height and blood pressure will be obtained through the patient's most recent VA visit from the electronic medical record. The Baseline will include a survey (completed before receiving PAL Intervention/Enhanced Usual Care). Veterans will receive accelerometers (described below). Electronic chart review will also occur at these time points. At 6 months, Veterans in the intervention arm will participate in a short qualitative interview as part of the RE-AIM evaluation Telephone Coaching Calls (Veterans in PAL Intervention arm only): Health coaches will use a counseling tool that also facilitates data collection.

Chart reviews (24 months post-baseline visit) to explore maintenance of weight and focus groups post-

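### For remote baseline visits, undefined resource materials are mailed with the consent forms, so Veterans may receive their allocated condition, or see their arm, before assent and baseline measures

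*Combined protocol and SAP*

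**What the plan says.** Under Study Arms/Randomization, "the PACT teams will be randomized at the provider level using a random number generator to either the PAL Intervention or Enhanced Usual Care" arms, so a Veteran's arm follows from his or her provider. The text just before it says that "recruitment will start the first quarter of Year 2", while PACT Team Training says that "PACT team staff will receive training sessions during Year 1 of the study". Identifying and Recruiting Veterans describes rolling recruitment ("we will continuously identify Veterans who meet the eligibility criteria below"): a letter, then a call to recruit, screen and book.

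Both arm descriptions offer a remote baseline visit. In the PAL description, a scale, a tape measure, "informed consent form documents, and the study resource materials will be mailed to the participant". In the Enhanced Usual Care description, "a scale, a tape measure for the waist circumference, the informed consent forms, and the resource materials will be mailed to the participant". In both, assent is then verbal, with the form read out by telephone or video. Data Collection says that remote weight and waist are also obtained that way.

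Data Collection gives one rule on order: "The Baseline will include a survey (completed before receiving PAL Intervention/Enhanced Usual Care"). No section defines the resource materials, gives separate mailing dates, or describes keeping the arm from recruiters or Veterans until baseline is complete.

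**The concern.** In a cluster trial that recruits individuals after the clusters are allocated, randomisation protects the comparison only if people join, and give their baseline data, without knowing their arm. A mailing that carries the arm's content ahead of assent opens two routes to bias.

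- **Who completes enrolment.** A Veteran who has booked a remote visit and then finds only handouts in the packet may drop out at a different rate from one expecting coaching.
- **What is recorded at baseline.** Answers on motivation, self-efficacy and diet can shift once weight management material has been read.

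The planned mixed model accounts for clustering and can adjust for measured baseline characteristics. It cannot correct differential enrolment on unmeasured traits, and it adjusts poorly for covariates that the allocated material has already altered.

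**Working it through.** The plan gives no figure to reproduce on this point, so the check is to put the passages in time order.

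**1. When is the arm fixed?** The documents do not say outright. Three facts point to allocation before recruitment: PACT training is in Year 1 and Veteran recruitment starts in Year 2; Veterans are identified on a rolling basis; and arm-specific content (tool and coach, or handouts) is delivered at the baseline visit itself. The last fact alone requires the arm to be known by that visit. Allocation before approach is a strong inference, not stated text.

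**2. What must arrive before a remote baseline?** The scale and tape measure must, because weight and waist are taken during the contact. The consent form is read aloud but is listed in the same mailing sentence. The resource materials stand in that sentence too, with no later date and no instruction to leave them unopened.

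**3. What are the resource materials?** They are undefined in both arms. In the Enhanced Usual Care description, the only candidates are the weight management handouts and the information on intensive VA programmes, and these are the control condition. In the PAL description, the MOVE! handouts are tailored to questionnaire responses, so that tailored set cannot be what is mailed beforehand.

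**4. Compare with Data Collection.** That section places the survey before either condition is received. For in-person visits the arm descriptions agree: consent, then survey, then tool and coach or handouts. For remote visits the mailing sentence, as written, allows the control condition to arrive first.

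**5. Does any reading of the undefined contents remove the problem?**

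| Packet contents | Consequence |
|---|---|
| Differ by arm | The arm can be inferred before assent and baseline |
| Same in both arms, with the control handouts | The control condition is received before baseline, against Data Collection |
| Neutral in both arms | No early exposure, but the plan does not say when remote Enhanced Usual Care Veterans receive their handouts |

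Each reading leaves a conflict or a gap.

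**6. Size.** An estimate needs the share of baselines done remotely, the difference between arms in loss after the packet arrives, and the weight-change difference between those lost and those kept. The documents give none of these. They say only that a remote visit is available when circumstances restrict in-person visits or when the Veteran prefers it.

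**The case against.** The strongest reply is that Data Collection already states the right order and that the mailing sentences are loose drafting. The two sentences are nearly the same in both arms, so the packet may be generic and identical. They also do not say that everything goes in one envelope on one day. This stands in part: arm-specific packets are not established. But a stated order is no safeguard if the mailing procedure can break it, and the control condition consists of mailable handouts.

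A second reply is that exposure is limited. The packet logically follows the recruitment call, so most of the refusal behind the expected 20% participation rate happens before it arrives. Consent materials are the same in both arms. The control content is standard, and the section on relevance to the VA reports an average MOVE! screening and referral rate of 94%, so early receipt is unlikely to move baseline weight much. All of this stands, and it narrows the point.

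A reader might go further and infer that in-person visits also reveal the arm, because staff "schedule the baseline visit which allows enough time for all intervention components to be completed", and PAL adds 20 + 30 = 50 minutes for tool and coach. The documents do not support this. The sentence sits in the general recruitment text and mentions neither arm nor slot length; one slot long enough for everyone fits it equally well. A reader might also infer that the two packets must differ because PAL handouts are tailored. That does not follow, since the tailored handouts cannot be in the advance mailing at all.

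**Conclusion.** The concern holds for remote baseline visits only. As written, the remote procedure can deliver the allocated condition, or disclose the arm, before assent, survey, weight and waist, and it conflicts with the order in Data Collection. The case is clearest for Enhanced Usual Care.

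The conclusion rests on two inferences: that providers are allocated before Veterans are approached, and that the resource materials include the handouts described for that arm. Both are well supported, but neither is stated.

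The possible effects are differential loss between booking and assent, and altered baseline survey answers. No figure in kilograms can be attached to this; any such figure would rest on invented inputs and an unknown remote share. Nor should the point be read as showing bias across the full 20% participation step or among in-person enrolees. It is a cheap improvement, not a threat to the trial's main comparison on present evidence.

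**What to change.** - In both remote-visit paragraphs under Study Arms/Randomization, specify an identical first packet for the two arms: scale, tape measure and consent form only.
- Send the resource materials, or have a sealed envelope opened, only after verbal assent, baseline survey, weight and waist are complete. List what those materials are in each arm.
- Cross-refer to Data Collection so that its order covers remote visits explicitly, and state when providers are randomised relative to Veteran recruitment.
- In Identifying and Recruiting Veterans, state that calls and booking use the same arm-neutral script in both arms.
- Report the numbers contacted, agreeing and consenting by arm, so that differential loss can be seen.

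The cost is a second small mailing or a sealed envelope for each remote enrolee, a short protocol edit and a count by arm at each recruitment step. Sample size does not change.

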## PAL INTERVENTION ARM: BASELINE VISIT

For Veterans in the PAL Intervention, they will need to complete the following (items 1 and 2 will be completed at the baseline visit). Average times to complete are included below based on pilot testing.

1. Complete the PAL tool (20 minutes)
2. Meet with a health coach and review materials with tailored educational materials (30 minutes)
3. Receive 10-12 telephone coaching calls from health coach (20-30 minutes each)
4. Follow up as needed with PACT teams for PC (varies)

Baseline Health Coach Visit – After completing the PAL tool, a health coach meets with the Veteran for approximately 30 minutes (based on our pilot study). All sessions will be audio-recorded for fidelity checks and health coach training if recording equipment is available. The health coaching manual will help the coaches to do the following tasks:

- Make initial goals into SMART goals (Specific, Measurable, Attainable, Relevant, Timely) using worksheets
- Encourage participation (using MI) in MOVE, TeleMOVE!, or other VA or community-based programs/gyms
- Teach how to self-monitor weight, diet, and PA behaviors via pedometer, food log, and/or weight management apps (e.g., MOVE! Coach on iPhones, My Fitness Pal on Androids)
- Provide brief MI and Brief Action Planning to address barriers and increase Veteran self-efficacy
- Facilitate meetings with PACT dietitian if needed
- Enter a report for PACT teams into CPRS summarizing the encounter (generated by the PAL tool)
- Communicate potential barriers/concerns to the PACT team
- Encourage utilization of MyHealtheVet
- After baseline visit, provide 10-12 telephone coaching calls (described below)

Telephone Coaching/Self-Monitoring Visit – To achieve sufficient intensity according to VA/DOD and USPSTF guidelines, we will incorporate 12 telephone coaching calls by a health coach over 12 months. Scheduled calls will occur two weeks and four weeks post-baseline, then once every month for the remainder of the study. PAL Intervention arm Veterans will receive a reminder call to self-monitor their weight, food intake, and PA for at least 3 days prior to the coaching call. Studies suggest that episodes of short, consistent self-monitoring (for 3 days) lead to weight loss and may promote better adherence. Health coaches will use self-reported self-monitoring data to determine goal adherence and counsel Veterans to encourage small changes. Data from health coaching sessions will be documented in REDCap, our research database. They will help Veterans create new goals when appropriate and use MI techniques to address barriers to behavior change. Veterans will be able to contact health coaches for additional support.

CPRS Research Note/Reminders– The PAL tool creates a provider report that the health coach will cut and paste into CPRS as a research note to summarize and communicate information to the Veteran's PACT team about the health coach session. This note generates a CPRS reminder for the PCP. The reminder facilitates documentation about whether the PACT team discussed goals and provided further counseling. This research note and reminder system will also be used to document both health coach telephone counseling and PACT counseling during future PC visits.

PACT Team Role – PACT teams randomized to the intervention arm will provide at least 3-5 minutes of counseling. They will choose who on the team counsels (based on formative data indicating variability in team member roles). They will document counseling with the help of CPRS reminders, provide brief MI to address barriers (depending on time and Veteran needs), and briefly discuss weight management goals during future PC visits. Each PACT team dietitian will co-sign the health coach CPRS note and will be available as a resource. Health coaches will attend PACT meetings to communicate the progress of enrolled Veterans. They will also communicate PACT team barriers to the PI.

Tailoring the PAL Intervention for Participants with Diabetes– We will use data from Veterans with diabetes from prior pilot studies (unpublished data) and input from our Executive Committee to develop additional diabetes-related content. We will also revise the health coach curriculum to include common counseling needs and concerns for patients with diabetes and linkages to diabetes resources at the VA. [name], RD, the MOVE! coordinator, and [name], a behavioral psychologist and Health Behavior Coordinator (HBC) at the VA NYHHS, both Co-Is, will help create the content and curriculum.

PACT Team Training – PACT team staff will receive training sessions during Year 1 of the study with follow up training by Drs. [name] (PI) and [name] (Co-I). As part of her role as HBC, [name] has provided the majority of RN care managers and PCPs 2-4 hours of MI training, as well as 6 hours of TEACH for Success Health Coaching Course during the past 4 years. We will build upon this VA training to include 5As-based obesity counseling and additional MI skills practice based on a 5As training intervention conducted by [name] and other adapted MI materials through CCMI. We will invite PACT staff to observe MOVE! sessions since we and others have found that clinicians often lack knowledge about program specifics which negatively impacts referrals. Training will also include indications and processes for referring to bariatric surgery. The first training will be approximately one hour with 2-3 subsequent trainings for 15-30 minutes. We will provide an overview of the 5As and the intervention components and practice brief MI (using role playing) to support Veterans' weight management goals and address barriers to change. Finally, we will assist in incorporating the health coach into each PACT team (e.g., include health coach at monthly PACT team meetings). We will use an academic detailing approach scheduled either one-on-one or in small groups so as not to interfere with VA clinical or administrative duties. This delivery approach is well accepted and similar to that used in the PROVE study.

